We propose doing such a study on Gulf veterans with GWI, characterized by a problem with widespread pain. Besides their pain, we will also assess the effect of VNS in alleviating migraine headache, another complaint of Gulf veterans, common in the presence of widespread pain. Importantly, we are partnering with a company that has made a hand-held device that allows for stimulation of the vagus nerve without the need for surgery; it works by the patient putting it on the skin overlying the vagus nerve in their neck and then turning it on for 120 second periods three times a day. The device is programmed to deliver only 6 bouts of stimulation per day – one to each side of the neck three times a day; it is then inactive until the next day. The fact that this device can be used without surgery and is non-invasive makes it extremely practical for use.

	Protocol Name:	Vagus Nerve Stimulation: A Non-Invasive Treatment to Improve the health of Gulf Veterans with Gulf War Illness
	Principal Investigator:	[name]
	Primary Contact Name/Contact Info:	[name]: [contact]
	Date Revised:	07/15/2019
	Study Number:	HSM# 16-00097

After collecting pre-treatment measurement of pain severity and headache severity, veterans will receive either the actual active VNS device or an inactive device, which does not stimulate the nerve. Veterans will use their device for ten weeks – providing similar information periodically over this period by responding to questions about the severity of their pain and headaches, They will then return to the Center for the final phase of the study where all veterans will receive active devices. Ten weeks later, they will return to the Center to provide information to allow the investigators to gain further knowledge as to the effectiveness of actual VNS in relieving pain – both throughout the body and in the head.

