**d) Study Timelines**

	Protocol Name:	Vagus Nerve Stimulation: A Non-Invasive Treatment to Improve the health of Gulf Veterans with Gulf War Illness
	Principal Investigator:	[name]
	Primary Contact Name/Contact Info:	[name]: [contact]
	Date Revised:	07/15/2019
	Study Number:	HSM# 16-00097

The VA part of the study will take up to 2 weeks. The ISMMS part of the study will consist of two parts – the blinded phase of the study which will be 10 weeks in duration and which will be followed by the open label phase of the study for an additional 10 weeks.

Allowing for scheduling, an individual will be in the study for up to 24 weeks.

The study is funded for three years. We expect to complete enrollment and data collection by the third quarter of the third year. We expect to have results in the final quarter of that year and will use them to prepare a proposal for funding a multi-site follow up trial to provide data to obtain FDA approval for use the device in treating the widespread pain of GWI.

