Encounter 11 – Phone Call: Within 65 ( $\pm 4$ ) days after Encounter 6 (Day 0) subject will receive phone call from study personnel to rate their widespread pain over past 24 hours on a 10-point VAS. .

Encounter 12 – Phone Call: Within 67 ( $\pm 4$ ) days after Encounter 6 (Day 0) subject will receive phone call from study personnel to rate their widespread pain over past 24 hours on a 10-point VAS.

Encounter 13 – Phone Call: Within 69 ( $\pm 4$ ) days after Encounter 6 (Day 0) subject will receive phone call from study personnel to rate their widespread pain over past 24 hours on a 10-point VAS.

Encounter 14 – Office Visit: Within 70 ( $\pm 4$ ) days after Encounter 6 (Day 0) subject will come to ISMMS. They will provide the 5th pain rating to arrive at the median pain rating. They will fill out same questionnaires they filled out on study Encounter 6 as well as the patient global measure of change and the measure of certainty, and will provide information about AEs and medication changes. They will again have the same brief medical evaluation as was done on Encounter #6 to provide data as to whether they fulfill criteria for GWI, CFS, IBS, MCS or FM. They will exit the blinded part of the study and return their original unit. Subjects who have completed at least 70% of diary entries will be given the active unit and will be trained on it again. They will be given new paper diaries and sent home. They will continue to use their electronic diary logon information to access their diary.

	Protocol Name:	Vagus Nerve Stimulation: A Non-Invasive Treatment to Improve the health of Gulf Veterans with Gulf War Illness
	Principal Investigator:	[name]
	Primary Contact Name/Contact Info:	[name]: [contact]
	Date Revised:	07/15/2019
	Study Number:	HSM# 16-00097

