	Protocol Name:	Vagus Nerve Stimulation: A Non-Invasive Treatment to Improve the health of Gulf Veterans with Gulf War Illness
	Principal Investigator:	[name]
	Primary Contact Name/Contact Info:	[name]: [contact]
	Date Revised:	07/15/2019
	Study Number:	HSM# 16-00097

*Statistical approach to data:* Safety data will be derived from every subject who used either sham or non-sham apparatus for any period of time. Therapeutic efficacy will be evaluated using both intent-to-treat (for all subjects who sign consent with those dropping out recorded as showing no change from baseline) and per protocol (for subjects who completed the 10 weeks of the blinded phase of the trial).

*Blinded study:* Our primary outcome variable will be post-intervention pain severity in the treatment versus sham condition, controlling for pain severity prior to randomization. We will define success for this variable if it decreases by 30% or more over the course of the trial. Five days of VAS data on pain severity will have been collected prior to randomization and during the last week of the 2.5-month stimulation period. For the primary analysis, these will be averaged to create a single pre-intervention and a single post-intervention pain severity score for each person. Post-intervention pain severity will be regressed on pre-intervention pain severity and intervention condition, using an analysis of covariance (ANCOVA) procedure.

A second analysis will use the pre and post measures of pain severity described above, along with pain severity assessments collected a third of the way and two thirds of the way through the 10 week blinded phase of the trial. These four equally spaced assessments over the 10 week study period will form the basis of a repeated measures analysis of variance in order to plot trajectories of pain as a function of treatment condition. We hypothesize a linear decrease in pain from baseline in the nVNS but not in the sham nVNS condition. Other variables (e.g., MIDAS, physical function part of the SF-36, CES-D) will be analyzed using the same general analytic approach; a simple *t*-test will be used to compare PGIC values between the groups at study end. We will define success criteria for PGIC and PF subscale of the SF-36 as scores of 5-7 and 0.5 SD improvement, respectively. Rate of drop out between the two groups while participating in the blinded phase of the trial will be tested for significance by Fisher’s test.

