In order to test whether subjects may have become aware of their treatment condition, we will also test for differences by condition in Measure of Certainty data collected at the end of the 2.5 month blinded treatment phase of the study.

*Open label data analysis:*

In addition to the analyses reported above, the open label methodology permits a test across all participants of improvement following 2.5 months of treatment. Regardless of condition, patients’ 2.5-month pain scores, at the end of the open label phase, will be compared to their baseline scores using a dependent samples *t*-test. It is possible that the sham group will show even greater improvement than those in the actually stimulated group had shown at the end of the blinded trial period. Any such increase in improvement would probably reflect a factor related to their knowing they were receiving the effective treatment – i.e., not blinded. Among patients originally in the active treatment condition, we can test for additional improvements beyond 2.5 months using a repeated measures analysis of variance (ANOVA) approach.

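### The open-label paired t-test is labelled improvement after 2.5 months of treatment, but as worded it pools about 20 weeks of active device in one arm with about 10 weeks in the other

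*Combined protocol and SAP*

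**What the plan says.** Section 5 h), under open label data analysis, states the purpose: "the open label methodology permits a test across all participants of improvement following 2.5 months of treatment". The rule that follows applies to patients of either condition: their "2.5-month pain scores, at the end of the open label phase, will be compared to their baseline scores using a dependent samples" t-test. Baseline is not defined for this test. In the blinded-study paragraph just before, the reference score is the pre-randomisation one ("controlling for pain severity prior to randomization"), so that is the natural reading.

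Two nearby sentences do distinguish the arms by exposure. One considers whether the sham group might improve more "than those in the actually stimulated group had shown at the end of the blinded trial period". The other says: "Among patients originally in the active treatment condition, we can test for additional improvements beyond 2.5 months".

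The schedule comes from other sections:

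- The Brief Summary describes a final phase "where all veterans will receive active devices".
- Section 5 d) has a 10-week blinded phase, "followed by the open label phase of the study for an additional 10 weeks".
- At Encounter 14 (day 70 ±4), section 5 f) says of the patients: "They will exit the blinded part of the study and return their original unit". Those with at least 70% of diary entries then receive an active unit.
- Encounter 22, which supplies the last of the five closing pain ratings, is at day 140 ±4.

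**The concern.** The purpose sentence and the operative rule agree only for patients who began on sham. For patients who began on active stimulation, the score at the end of the open-label phase follows twice the labelled duration. An analyst who follows the text would use day 140 for everyone and could report the result as the change after 2.5 months of nVNS.

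A second problem comes with the pre-randomisation baseline. The sham arm's change then also includes whatever happened during 10 weeks of sham. Section 2 of the protocol accepts that the earlier uncontrolled results could have been placebo responding, and that is the reason for the sham arm here. A figure presented as the effect of 2.5 months of active treatment should not absorb that component unlabelled.

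The figure could also be carried forward, since section 5 d) says the results will be used to prepare a multi-site trial proposal.

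**Working it through.** **Inputs.** Active device from day 0 in the original active arm and from day 70 ±4 in the original sham arm. Final score at day 140 ±4. Half of the evaluable patients in each arm, target 40 (section 5 c). The plan treats 10 weeks and 2.5 months as the same period.

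**Active-device time at the final score** (elapsed days, completers)

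| Original arm | Formula | Days | Range with windows |
|---|---|---|---|
| Sham | 140 − 70 | 70 (10 weeks) | 136 − 74 = 62 to 144 − 66 = 78 |
| Active | 140 − 0 | 140 (20 weeks) | 136 to 144 |

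The plan's 2.5 months is reproduced for the sham arm and not for the active arm. The ranges do not overlap. With equal arms, the pooled mean is (140 + 70)/2 = 105 days = 15 weeks, with a range of (136 + 62)/2 = 99 to (144 + 78)/2 = 111 days.

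**Effect on the estimate.** Define four mean changes in pain score:

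- DA: original active arm, pre-randomisation to Encounter 14
- L: original active arm, Encounter 14 to 22
- S: original sham arm, pre-randomisation to Encounter 14 (on sham)
- DS: original sham arm, Encounter 14 to 22 (on active)

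Pre-randomisation baseline, equal arms:

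- As written: [(DA + L) + (S + DS)]/2
- Aligned on the first 10 weeks of active device: (DA + DS)/2
- Difference: (L + S)/2

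This does not require DA = DS. The two versions agree only if L + S = 0. Each 1 point of L + S moves the pooled mean by 0.5 point on the 0–10 scale. If both L and S are improvements, the test as written shows a larger improvement than the aligned one.

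Encounter 14 baseline instead:

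- As written: (L + DS)/2
- If DA = DS = D (an assumption): (D + L)/2

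Here the active arm starts from an already treated score. If L were 0, the result would be D/2, half the 10-week change.

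The documents give neither L nor S, so size and direction stay open.

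**The case against.** The strongest reply is that 2.5 months names a phase, not a cumulative exposure. Section 5 h) uses the term for the blinded period as a whole, sham patients included. The disputed score could then be the one taken after the 2.5-month open-label phase, when both arms are on the active unit. This does not rescue the rule. With a pre-randomisation baseline the interval is 20 weeks in both arms and takes in the sham phase. With an Encounter 14 baseline the interval is 10 weeks, but for the active arm it is the second 10 weeks of treatment.

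It can also be said that the authors knew the exposures differ, since they plan a separate analysis of the active arm past 2.5 months. That is true, and alignment may well have been intended. Yet nothing assigns the day-70 score to the active arm for the t-test.

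One might expect L to be small, because section 2 suggests that self-reported symptoms level off. That remark concerns 3 months of stimulation, later than week 10, in 12 evaluable patients with implanted devices. It says nothing about S.

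Several limits do stand:

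- The label fits the sham arm only as time on active device. With a pre-randomisation baseline, that arm's measured change spans 20 weeks.
- The exposure figures are elapsed time, not stimulation delivered, because the 70% device-use rule is not enforced.
- Patients below 70% diary completion and withdrawn patients do not enter the open-label phase. The formulas describe completers. If the intent-to-treat rule of recording dropouts as unchanged were applied here, they would not hold as given.
- The plan contains no reporting language for this test, so the mislabelled report is a likely consequence, not a stated one.

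**Conclusion.** The concern holds, as a minor one. Read as written, the test does not estimate improvement after 2.5 months of active treatment: about half of the pooled patients have had about 20 weeks of active device, and the pooled mean is 15 weeks, not 10. The exposure figures rest only on the plan's schedule. The 15-week mean and the (L + S)/2 difference also assume equal numbers of completers per arm, and the latter a pre-randomisation baseline. Whether the discrepancy matters numerically cannot be told from the documents, though the plan itself leaves room for change after week 10 by proposing to test for it. The analysis is not among the endpoints in section 5 e) and has no control group, and the primary blinded comparison does not depend on it.

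**What to change.** Choose one of the following and state the baseline explicitly.

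1. **Align on first active stimulation and report by original arm.** Active arm: the five-rating score ending at Encounter 14 against the pre-randomisation score. Sham arm: the score ending at Encounter 22 against the score ending at Encounter 14. Keep the planned analysis of the active arm beyond 2.5 months, and label all of these estimates uncontrolled.
2. **Keep the pooled day-140 test** and describe it as change from entry to end of study, with no reference to 2.5 months of treatment.

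Both are changes of analysis wording only, since the scores ending at Encounters 6, 14 and 22 are already collected. Under option 1, with about 20 patients per arm, standard errors are about √(40/20) = 1.4 times those of a pooled 40, if the changes have similar standard deviations. Pooling the two aligned changes is an acceptable variant that avoids this loss. In either form the active-arm estimate is blinded and the sham-arm estimate is open-label, so both still contain non-specific change and should be read accordingly. Option 2 has no statistical cost but gives no 2.5-month estimate.

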**i) Provisions to Monitor the Data to Ensure the Safety of Subjects**

	Protocol Name:	Vagus Nerve Stimulation: A Non-Invasive Treatment to Improve the health of Gulf Veterans with Gulf War Illness
	Principal Investigator:	[name]
	Primary Contact Name/Contact Info:	[name]: [contact]
	Date Revised:	07/15/2019
	Study Number:	HSM# 16-00097

**Part I: Elements of a Data and Safety Monitoring Plan**

1. List the name(s) of the individual(s) at MSSM who will be responsible for data and safety monitoring of this study. For each individual, indicate their role, name, title, and department information. The Principal Investigator may be the only monitor of a study.

If the qualifications of an individual to serve as a monitor are not contained in the PPHS application, they must be added to the DSMP either as a narrative description or as a CV.

**Name: [name]: Independent Clinical Data/Study Monitor**

**Mailing Address: M Squared Associates; [name]**

**[contact]**

**Email: [[contact]](mailto:[contact])**

2. The hand held, patient controlled, transcutaneous nVNS device presents minimal risk to the user. That interpretation can be made from the fact that the device has been now used with hundreds of research subjects and by thousands of patients in Europe and Australia (where it has been approved for sale) with minimal side effects. There has never been a serious adverse effect attributed to its use.
3. The specific items that will be monitored for safety include adverse events, subject's compliance with the protocol, and drop outs.
4. Since no clinical trial using nVNS has ever had to be halted, we doubt this will happen herein but should it happen that information will be passed onto appropriate DOD personnel monitoring the Human Studies regulatory issues related to this trial.
5. Data accuracy and completeness: The data collection tool for this trial will be a validated electronic data capture (EDC) system using eCRFs. Subject data necessary for analysis and reporting will be entered into a validated database or data system using source documentation

	Protocol Name:	Vagus Nerve Stimulation: A Non-Invasive Treatment to Improve the health of Gulf Veterans with Gulf War Illness
	Principal Investigator:	[name]
	Primary Contact Name/Contact Info:	[name]: [contact]
	Date Revised:	07/15/2019
	Study Number:	HSM# 16-00097

available at the site. The PI is to maintain all source documents as required by the protocol, including laboratory results, Subject Case Report Forms, supporting medical records, documentation of all study visits and telephone calls and Informed Consents. The source documents will be used at monitoring visits to verify information submitted on the Subject Case Report Forms.

5. Duties of the Independent Medical Monitor: Both the study PI, [name], and the Independent Medical Monitor, [name], will review any unanticipated problems involving risk to subjects or others, serious adverse events and all subject deaths associated with the protocol and provide an unbiased written report of the event. [name] will transmit information concerning such an event to the IRB with his input as to whether the event was related to the study device; this material will also be given to [name] to allow her to comment on whether she concurs with the details of [name] report. Reports for events determined by either [name] or [name] to be possibly or definitely related to participation and reports of events resulting in death will be promptly forwarded to the FDA, to the device manufacturer, electroCore, and to USAMRMC ORP HRPO. The independent Medical Monitor has the authority to stop the research protocol in progress, remove individual human subjects from the research protocol, and take whatever steps are necessary to protect the safety and well-being of human subjects until the IRB assesses the Independent Medical Monitor's report. [name] and [name] will meet biannually.

7. Duties of the Independent Clinical Study Monitor: The Clinical Study Monitor will assure that complete, accurate and timely data are submitted, that protocol requirements are followed, and that the safety and rights of subjects is being protected. This will include on-site checking of the eCRF for completeness and clarity, crosschecking with source documents, and clarification of administrative matters as follows:

- Ongoing compliance with the study protocol.
- Ongoing compliance with any conditions of approval of the reviewing IRB and the IDE regulations.
- Maintenance of complete and accurate study records including quality control checks on CRFs
- Continued acceptability of the site’s facilities.

All monitoring tasks will be carried out in such a manner as to protect patient confidentiality and protected health information. Data problems will be addressed in contacts with the study staff. [name] will meet with [name] on a quarterly basis.

8. If a temporary or permanent suspension of this study should occur, in addition to the PPHS, [name] will report this immediately to DoD and to electroCore LLC.

**j) Withdrawal of Subjects**

	Protocol Name:	Vagus Nerve Stimulation: A Non-Invasive Treatment to Improve the health of Gulf Veterans with Gulf War Illness
	Principal Investigator:	[name]
	Primary Contact Name/Contact Info:	[name]: [contact]
	Date Revised:	07/15/2019
	Study Number:	HSM# 16-00097

- The subject is non-compliant with the study protocol or follow-up requirements;
- The subject withdraws consent;
- The Investigator decides that it is in the subject’s best interest.

Subjects who withdraw or are withdrawn will be asked, but not obligated, to provide a final set of data via questionnaires. These subjects will not be allowed to participate in phase 3 of the study, the open label part. Subjects who are randomized but withdraw consent or are withdrawn prior to first treatment with the study device will be replaced.

**6. Risks to Subjects**

The potential risks and complications are anticipated to be mild to moderate in nature, and are anticipated to resolve shortly after discontinuation of the stimulation procedure without medical intervention or clinical sequelae. The following risks and complications have been associated with other VNS devices and may potentially occur with gammaCore:

- Muscle twitching and/or contractions to the face/head/neck including facial droops and/or lip pull
- Light-headedness or dizziness
- Headaches
- Shortness of breath (dyspnea)/hoarseness or change in voice tone during treatment/cough
- Irregular heart beat (arrhythmia)
- Metallic taste
- Gastrointestinal discomfort or nausea

Risks that are also potential anticipated adverse events resulting from the use of the nVNS device include, but are not limited to:

- Application site discomfort and/or local pain in the face/head/neck area including toothaches
- Application site irritation/redness
- Muscle twitching and/or contractions, face/head/neck area including facial droops and/or lip pull
- Headache/Migraine
- Tingling, pricking or a feeling of “pins and needles” on the skin where the device is applied (paresthesia/dysesthesia)

Should a volunteer become pregnant, she will be exited from the study as pregnancy is an exclusion.

**6) Provisions for Research Related Harm/Injury**

[name] and [name] will be available to deal with any adverse event that may come from this study. Research participants will have the phone numbers of both these investigators and can be called as needed.

	Protocol Name:	Vagus Nerve Stimulation: A Non-Invasive Treatment to Improve the health of Gulf Veterans with Gulf War Illness
	Principal Investigator:	[name]
	Primary Contact Name/Contact Info:	[name]: [contact]
	Date Revised:	07/15/2019
	Study Number:	HSM# 16-00097

If a problem arises for a veteran not living near ISMMS, the investigators will get in touch with the research participant’s doctor.

If a subject is injured or made sick from taking part in this research study, medical care will be provided. Generally, this care will be billed to the subject or the subject’s insurance in the ordinary manner, and the subject will be responsible for all treatment costs not covered by his/her insurance, including deductibles, co-payments and coinsurance. This does not prevent the subject from seeking payment for injury related to malpractice or negligence.

